9.7.2 Main analyses

The main analysis will cover the prescribing and monitoring patterns of oral retinoids during the pre- and post- implementation periods in females of childbearing age (13-49 years of age, inclusive) to meet the primary study objective. The analysis will be descriptive in nature. The first oral retinoid prescription of a treatment episode will be considered as exposure start date for the analyses of treatment episodes.

Measures related to the PPP

The following analyses will be performed:

- Laboratory pregnancy tests
 - Percentage of patients with laboratory pregnancy test performed at treatment start (up to 7 days before exposure start date)
 - Percentage of patients with laboratory pregnancy tests performed during treatment
 - Percentage of patients with laboratory pregnancy tests performed monthly according to the SmPC during treatment
 - Frequency of laboratory pregnancy tests during treatment, by month of treatment
 - Percentage of patients with laboratory pregnancy tests performed after treatment stop
 - For all retinoids: percentage of patients with laboratory pregnancy test performed within two months after treatment stop
 - For acitretin: performance of laboratory pregnancy tests beyond 1 month up to 3 years after treatment stop (depending on the length of individual follow-up of patients)
- Contraceptives

- Percentage of patients with prescription of hormonal contraceptives before treatment start (up to 3 months before the exposure start date or longer depending on the type of contraceptive)
- Percentage of patients with use of IUDs before treatment start (up to 5 years before exposure start date)
- Percentage of patients with concomitant use of contraceptives (hormonal contraceptives and / or IUD) during treatment
- Percentage of patients with use of contraceptives (hormonal contraceptives and / or IUD) within two months after treatment stop
- For acitretin: percentage of patients with use of contraceptives (hormonal contraceptives and / or IUD) beyond 1 month up to 3 years after treatment stop (depending on the length of individual follow-up of patients)
- Periodicity of oral retinoid prescriptions
 - Time interval between prescription dates for oral retinoid prescriptions during treatment (in days)
 - Proportion of oral retinoid users with monthly prescription intervals during treatment

It is aimed to include all patients with oral retinoid prescriptions in the analyses. However, a history of at least 3 months is necessary to cover prescriptions and laboratory pregnancy tests before treatment initiation. Analyses after treatment initiation will be performed for the following scenarios: (a) patients with a follow-up available covering the treatment episode and (b) patients with a follow-up beyond the treatment episode of at least 2 months.

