- an ‘acknowledgement form’ to confirm that appropriate advice has been given to patients;

- a ‘patient reminder card’ stating that the medicine must not be used during pregnancy and including information about pregnancy testing and the need to use effective contraception.

The PPP addresses the issues of effective contraceptive use, pregnancy testing, and rigorous monitoring to the treating physician (i.e., dermatologist or GP in some countries after first prescription). In fact, the difference between the implemented PPP before and after the implementation of the updated RMMs is relatively small (see Table 1). The measures of the of the PPP are similar in the countries of interest for this study.

The updated RMMs include updated educational material (EM), in some countries patient reminder card and pictogram on the outer package, and in addition, the redistribution of direct healthcare professional communication (DHPC).

Differences in the set of implemented tools may exist between countries due to the requirements of local authorities.

Table 1 Measures of the PPP before and after the newly implemented, updated RMMs

Active substance	PPP	Contraception			Pregnancy test			Days' supply/Length of prescription
		Before	During	After	Before	During	After	
Acitretin	Old ¹	Yes	Yes	3yrs	Yes	Monthly	3yrs	Limited to 30d
	New ²	1mo	Yes	3yrs	Yes	Ideally monthly	3yrs	Ideally limited to 30d
Alitretinoin	Old ¹	1mo	Yes	Yes	Yes	Monthly	5wks	Limited to 30d
	New ²	1mo	Yes	1mo	Yes	Ideally monthly	1mo	Ideally limited to 30d
Isotretinoin	Old ¹	1mo	Yes	1mo	Yes	Monthly	5wks	Limited to 30d
	New ²	1mo	Yes	1mo	Yes	Ideally monthly	1mo	Ideally limited to 30d

d: day(s); mo(s): month(s); yr(s): year(s)

¹ Summary of product characteristics for acitretin, alitretinoin, and isotretinoin in countries of interest (i.e., France, Germany, Spain, and Sweden); for the time period 2012-2017

² Annex to the Amendments to relevant sections of the Product Information from 22 March 2018

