9.7.1 General Considerations

Given the study objectives the analyses will be mainly descriptive and will be conducted by country, by active substance and study time periods (both pre-implementation periods and post-implementation period). To allow for analysis across all data sources used in the study, a meta-analytic approach will be used to assess and pool the results from the four study countries together for each active substance (see 9.7.3.4).

The analyses will be provided for the overall class of oral retinoids and for the single active substances. Categorical variables will be presented as counts (n), proportions (%) with CI where relevant as for parameters used to address the primary objective and for the comparison of the incidence of exposed pregnancies. Continuous variables will be presented as means with standard deviation (SD) and as medians with interquartile range (IQR), where appropriate.

Changes in the reimbursement policy for contraceptives in the healthcare systems of the study countries will be considered to discard any differential misclassification of exposure.

The statistical unit will be the oral retinoid treatment episode and patient as well as prescription where appropriate. Patients who have multiple treatment episodes of oral retinoid use will be entered the cohort for analysis more than once.

The term “use” in the context of the analysis refers to the prescription or dispensing of drugs or IUD.

In the analysis, prescriptions of patients will be followed from the exposure start date to censoring date, i.e., transfer out of the database incl. death or the end of the study period, whichever comes first.

Statistical analyses will follow the tables shells validated by the MAH consortium and will be displayed using tables, listings and/or graphs. The statistical analysis will be conducted using SAS or an equivalent statistical analysis software. A detailed statistical analysis plan (SAP) will be prepared prior to data extraction.

The statistical results of all target countries and all active substances will be presented in a single report.

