9.7.3.4 Meta-analysis

To account for any differences between the databases with regard to their format and to allow for differences in the population of patients treated with isotretinoin, acitretin, and alitretinoin, and differences in adherence to PPP measures in those populations, a meta-analytic approach will be used to combine the data. Specifically, drug- and country-specific estimates for the primary outcome measures will be assessed. In case of high heterogeneity between country-specific estimates for (a) certain active substance(s), an appropriate random-effect method will be used to derive a pooled estimate. In addition, the sensitivity of the overall pooled estimates to the inclusion or exclusion of certain country-specific estimates will be assessed. In some instances, it may not be appropriate to pool the data, and in such cases country-specific estimates will be excluded from the pooled estimate and presented separately.

9.7.3.5 Trends in the prescribing and monitoring practice of oral retinoids with respect to measures of the PPP

To identify ongoing trends in the countries of interest, ITS analysis using segmented regression will be performed in case the conditions for this analysis will be met (such as the number of time points in the pre-and post-implementation periods [at least 6 timepoints per period] and the number of observations per timepoint [at least 100] is available). Using ITS analysis, data will be evaluated at multiple time points before and after an intervention in order to detect whether or not an intervention had a significantly greater effect than any underlying trend.

The ITS analysis can assess the following key parameters:

- Proportion of episodes with contraception use for the month before treatment start
- Proportion of episodes with continuous concomitant use of contraception during the entire treatment episode
- Proportion of episodes with laboratory pregnancy tests at treatment start (up to 7 days before start date of oral retinoid prescription)
- Proportion of episodes with monthly laboratory pregnancy tests during treatment

A final decision on key parameters and time points for ITS analysis will be made based on results of analyses for primary outcomes. ITS analysis will be conducted for the outcomes only if sufficient data will be available for reliable results.

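### The main before-treatment contraception measure counts any prescription in a look-back of 3 months or longer, so it cannot show whether recorded contraception was in force for the month before start

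*Protocol*

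**What the plan says.** Protocol section 9.7.2 lists two before-treatment contraception measures:

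- Hormonal methods: "Percentage of patients with prescription of hormonal contraceptives before treatment start (up to 3 months before the exposure start date". The full window is "up to 3 months before the exposure start date or longer depending on the type of contraceptive".
- Intrauterine devices: "Percentage of patients with use of IUDs before treatment start (up to 5 years before exposure start date", with the bracket closing there.

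Section 9.7.1 defines use as a record, not as days covered: the term "in the context of the analysis refers to the prescription or dispensing of drugs or IUD".

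The programme element is in section 7.1, Table 1, "Measures of the PPP before and after the newly implemented, updated RMMs". Its contraception columns read before, during, after. The old acitretin row is "Acitretin Old ¹ Yes Yes 3yrs" and the new one is "1mo Yes 3yrs Yes Ideally monthly 3yrs". So the before-treatment entry for acitretin moves from an unspecified yes to one month. For alitretinoin and isotretinoin it is one month under both programmes.

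Section 9.7.3.5 lists, as a candidate for the interrupted time series (ITS), "Proportion of episodes with contraception use for the month before treatment start". That analysis needs at least 6 time points per period and at least 100 observations per time point. Its parameters are settled after the primary results are known. The abstract nevertheless describes the ITS as addressing the study's primary outcomes.

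**The concern.** The primary objective compares key programme elements before and after the update, and contraception before treatment is one of them. Table 1 expresses that element as a duration. The main measure asks only whether a record exists somewhere in a window at least three times as long. It can therefore stay still while adherence to the one-month element moves, or move while adherence stays still.

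Other measures in section 9.7.2 do follow the requirement they assess. Pregnancy tests during treatment are judged against a monthly schedule, and retinoid prescriptions against monthly intervals. Before-treatment contraception has no matching measure in the main analysis. At stake is whether the study can describe adherence to the one-month element for any substance and, for acitretin, whether it can detect a response to the one before-treatment contraception entry that changed.

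**Working it through.** **1. What the definition accepts.** Let d be the days from a prescription to retinoid start and S the days of supply. The main measure is positive for any d inside the look-back. Cover from a single supply over the 30 days before start needs d ≥ 30 and d ≤ S.

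- First prescription at d = 1: positive, with one day of cover before start.
- 28-day pack at d = 89: positive, although supply ended 89 − 28 = 61 days before start.
- 84-day supply at d = 40: positive, with the whole month covered.

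All three count the same.

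**2. How far the two definitions can differ (assumed timing).** The protocol gives no timing data. Suppose one first prescription per woman, spread evenly over days 1 to 90. All count under the main measure. Those begun at least 30 days ahead are days 30 to 90, 61/90 = 68%. Those with the whole month covered are:

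| Supply | Qualifying days | Share |
|---|---|---|
| 28 days | none | 0% |
| 84 days | 30 to 84 | 55/90 = 61% |
| 90 days | 30 to 90 | 61/90 = 68% |

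**3. What a before-after comparison would show (assumed shift).** The protocol's precision figure reproduces: 1.96² × 0.5 × 0.5 / 0.05² = 384.2, rounded up to 385. It is not in dispute and serves here as an illustrative number per period. Suppose 50% have a prescription in the window in both periods, and among them the share begun at least 30 days ahead (and still in supply) rises from 40% to 60%.

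- Main measure: 50% and 50%, difference 0.
- Month-before measure: 0.5 × 0.4 = 20% and 0.5 × 0.6 = 30%, difference 10 points.
- Power for 20% against 30%, two-sided 5%, 385 per period: null standard error √(2 × 0.25 × 0.75/385) = 0.0312; alternative √((0.16 + 0.21)/385) = 0.0310; z = (0.10 − 1.96 × 0.0312)/0.0310 = 1.25, so power is about 89%.

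**4. Where the requirement changed.** From Table 5, acitretin patients in Germany, Spain and Sweden are 153 + 281 + 442 = 876 of 3,729 + 4,842 + 20,580 = 29,151, or 3.0%. In France only boxes are known, unrestricted by age or sex: 195,417 of 1,041,500, or 18.8%.

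**5. Whether the ITS fills the gap for acitretin.** Its conditions imply at least 6 × 100 = 600 observations per period. Scaling the three-year acitretin counts to the two-year post-implementation period (× 2/3) gives about 102 in Germany, 187 in Spain and 295 in Sweden. Reading observations as episodes, even Sweden would need 600/295 ≈ 2 episodes per patient. French patient numbers are unknown. A class-level ITS would consist overwhelmingly of isotretinoin.

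**6. The ITS parameter is itself unsettled.** Because use means a record, it can be read as a record dated within the last month. For continuous users refilling every 84 to 91 days, that would find only 30/84 = 36% to 30/91 = 33%. Shortening the prescription window is therefore not the remedy.

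**The case against.** The best defence is that the look-back is a search period, not a test of adherence. The allowance for longer periods by type ties the window to how long a method lasts, and three months is sensible for women on three-month supplies. Rules for run-out and permitted gaps are normal SAP content, and the SAP is not shown. The protocol also knows the month-before measure, since it is in section 9.7.3.5.

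Part of this stands. The look-back length is reasonable and should stay, and the gap rule can go in the SAP. But the added words only lengthen the window; they set no lead time and require no cover at start. The protocol itself fixes the main measure as a percentage with a record. The month-before parameter is secondary, conditional, and confirmed only after the primary results.

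Three stronger readings are tempting and are not supported:

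- *That the study would miss the programme's effect.* The before-treatment rule changed for acitretin only, and section 7.1 calls the overall old-to-new difference relatively small. The measure does respond when women move from no recorded contraception to some before start. It is blind only to shifts inside the window.
- *That about a third of positives are too late.* The last 30 of some 91 days is a third of the window's length, not of the women. It becomes a share of women only if first prescriptions are evenly spread, and it does not apply to established users.
- *That the measure overstates adherence.* Section 9.9.2 expects contraceptive use to be under-recorded in both periods, which pulls the other way. The net direction is unknown.

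**Conclusion.** The point holds in a limited form. As written, the main before-treatment measure cannot show whether recorded contraception was in force for the month before start, for any of the three substances. This follows from the definitions and needs no assumption. For alitretinoin and isotretinoin the loss is in describing adherence to an unchanged element. For acitretin it also means a response to the changed element could go unseen, in a group that is 3.0% of counted patients in three countries and of unknown size in France.

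The size of any missed change cannot be taken from the protocol. The 50% against 50% and 20% against 30% comparison rests on assumed prevalence and timing, and shows only that a change large enough to detect with 385 per period could leave the main measure unmoved. The main measure and the month-before ITS parameter also differ, although the abstract presents the ITS as covering the primary outcomes. This should be corrected before extraction, but it does not invalidate the study.

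**What to change.** In section 9.7.2, keep the look-back of 3 months or longer as the way to find supply. Add as a main measure the percentage of episodes with recorded contraceptive coverage over the 30 days before exposure start.

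- Derive coverage from prescription or dispensing date plus days' supply, pack size or device duration. Section 9.3.2 already extracts date and type, and pack size or days' supply for hormonal methods.
- Pre-specify a permitted gap.
- For Sweden, state that supply is inferred from package size. Section 9.4.3.1 says days' supply is not recorded there and prescribed dose is available only as free text.
- Use the same definition in section 9.7.3.5, and report it by substance.
- Keep the any-prescription percentage as a looser companion measure.

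The cost is some protocol and SAP wording and one derived variable. Section 9.7 allows the analyses to be revised, and extraction is planned to start in July 2021. Reported percentages will be lower than on the any-prescription measure. Late refills, leftover packs and inferred supply will misclassify some covered women as uncovered, so the report should show both measures side by side.

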9.3.2 Patient age and prescribing and monitoring practices

To describe the prescribing and monitoring practices of oral retinoids before and after the dissemination of risk minimisation measures, the following variables will be considered:

- Patient age
- Specialty of prescriber (not for France)
- Records of sterilisation in the medical history
- Indication for oral retinoid prescription (only available for in-hospital prescriptions in France)
 - Diagnoses coded by International Classification of Diseases (ICD)-10 (i.e., acne, severe hand eczema, psoriasis, or other dermatological conditions oral retinoids are indicated, for code list please refer to Appendix 3)
- Contraceptives before, during and after oral retinoid treatment
 - Prescription of hormonal contraceptives (date of prescription/dispensing, type, pack size or days' supply)
 - Prescription of intrauterine devices (IUD) (date of prescription/dispensing or procedure)
- Laboratory pregnancy tests – based on availability - before, during and after oral retinoid treatment
 - Laboratory pregnancy tests (blood or urine) recorded in the databases (type, if available, and date of test)
 - Records (ICD-10 codes related to an exam) which document the performance of a laboratory pregnancy test (date of record)

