Annex 3.2: List of ICD-10

Identification of indication associated with oral retinoids (lists may be subject to amendment or revision during study conduct)

Substance	Indication	ICD-10 codes
Acitretin	Extensive and severe refractory forms of psoriasis	L40: Psoriasis L40.0: Psoriasis vulgaris L40.1: Generalized pustular psoriasis L40.3: Pustulosis palmaris et plantaris L40.9: Psoriasis unspecified
	Pustulous psoriasis of the hands and feet	
	Lichen ruber planus of skin and mucous membranes	L43: Lichen planus
	Severe congenital ichthyosis and ichthyosiform dermatitis	Q80: Congenital ichthyosis
	Other severe and refractory forms of dermatitis characterised by dyskeratosis and/or hyperkeratosis	L30: other and unspecified dermatitis
Alitretinoin	Adults who have severe chronic hand eczema that is unresponsive to treatment with potent topical corticosteroids	L20: Atopic dermatitis L23: Allergic contact dermatitis L24: Irritant contact dermatitis L25: Unspecified contact dermatitis L30: other and unspecified dermatitis L85.1: Acquired keratosis (keratoderma) palmaris et plantaris
Isotretinoin	Severe forms of acne (such as nodular or conglobate acne or acne at risk of permanent scarring) resistant to adequate courses of standard therapy with systemic anti-bacterials and topical therapy	L70: Acne

ICD-10 codes for the identification of contraceptive management, laboratory pregnancy testing and outcome of delivery (list may be subject to amendment or revision during study conduct)

Category	ICD 10 code	Description
Complications	T83.3	Mechanical complication of intrauterine contraceptive device
Health services in circumstances related to reproduction	Z30.0	General counselling and advice on contraception
	Z30.1	Insertion of (intrauterine) contraceptive device
	Z30.4	Surveillance of contraceptive drugs
	Z30.5	Surveillance of (intrauterine) contraceptive device
	Z30.8	Other contraceptive management
	Z30.9	Contraceptive management, unspecified
	Z97.5	Presence of (intrauterine) contraceptive device
	Z32.0	Pregnancy, not (yet) confirmed
	Z32.1	Pregnancy, confirmed
	Z33	Pregnant state, incidental
	Z34	Supervision of normal pregnancy
	Z35	Supervision of high-risk pregnancy
	Z36	Antenatal screening
	Z37	Outcome of delivery
	Z38	Liveborn infants according to place of birth
	Z39	Postpartum care and examination
Pregnancy and pregnancy outcomes	O00-O99	Pregnancy, childbirth and the puerperium

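### IUD use before treatment is any IUD record in the previous 5 years, so a later recorded removal, expulsion, pregnancy or delivery does not stop a woman counting as a user

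*Protocol*

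**What the plan says.** Among the contraceptive measures of section 9.7.2 is "Percentage of patients with use of IUDs before treatment start (up to 5 years before exposure start date". Section 9.7.1 fixes the key word: "The term “use” in the context of the analysis refers to the prescription or dispensing of drugs or IUD".

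Section 9.3.2 lists what is extracted for IUDs: "Prescription of intrauterine devices (IUD) (date of prescription/dispensing or procedure". For hormonal contraceptives the same section also asks for pack size or days' supply, which gives their cover an end. For IUDs it asks for no removal or expulsion date.

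A second measure in 9.7.2 is "Percentage of patients with concomitant use of contraceptives (hormonal contraceptives and / or IUD) during treatment", and a third covers the two months after treatment stop. Neither says how far back an IUD record may lie.

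Annex 3.2 has one table headed "ICD-10 codes for the identification of contraceptive management, laboratory pregnancy testing and outcome of delivery". Under its own category, Complications, the table includes T83.3, "Mechanical complication of intrauterine contraceptive device". The protocol does not say what that code is for.

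**The concern.** A look-back of several years is reasonable for a device that stays in place for years. It needs an ending rule, because a device can be removed or expelled, and a later pregnancy is strong evidence that an earlier device was no longer protecting. The protocol supplies the window and the definition of use but no ending event.

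The measure is one of those by which the study judges adherence to the contraception element of the programme. Counting women whose own records show that the device is gone makes adherence look better than the data source supports. The limitations in section 9.9.2 discuss only underestimation of contraceptive use, so a reader of the final report would not be warned of this error.

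**Working it through.** **1. The rule applied to one case.** Take a woman with an IUD record 4 years before exposure start and a recorded delivery 2 years before it.
- Window (9.7.2): 4 years is less than 5, so the record falls inside.
- Definition (9.7.1): a record exists, so it is use.
- Delivery: 9.3.3 searches for this record for the pregnancy objective, but no text links it to the contraceptive measures.
- Result: she is in the numerator. The same holds after a recorded removal or expulsion.

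**2. Whether the records exist.** Table 3 lists pregnancy as available in all four sources, and Annex 3.2 already lists Z33 to Z39 and O00 to O99. The earliest exposure start in the comparison is July 2014, and 5 years earlier is July 2009. Table 3 gives data from 2009 (France), 2004 (Germany) and 2005 (Spain and Sweden), so the look-back years are covered in principle. The protocol names no removal code, so the availability of removal records is unknown.

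**3. Size.** The protocol has no figure on this point to reproduce. As an assumption, spread the counted IUD records evenly over the 5 years and let a constant share *d* of devices be discontinued each year. The share of counted users without the device is then

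1 − mean of (1 − d)^t over 0 to 5 years = 1 − [1 − (1 − d)^5] / [−5 ln(1 − d)].

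| d per year | (1 − d)^5 | Share without device | If 10% are counted as users, percentage with device |
|---|---|---|---|
| 5% | 0.774 | 0.118 | 10 × 0.882 = 8.8% |
| 10% | 0.590 | 0.223 | 10 × 0.777 = 7.8% |
| 15% | 0.444 | 0.315 | 10 × 0.685 = 6.8% |

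As a cross-check, a continuous rate *r* gives 1 − (1 − e^(−5r)) / (5r) = 0.115, 0.213, 0.296 and 0.368 for r = 5, 10, 15 and 20% per year. If 5 to 20% of women have an IUD record, the overstatement runs from 0.05 × 0.115 = 0.6 points to 0.20 × 0.368 = 7.4 points.

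These figures size all discontinuation. If a share *q* of the discontinued devices has a recorded ending event, the correctable part is *q* times the share in the table. The documents say nothing about *q*, so at d = 10% the correctable part lies anywhere from 0 to 22% of counted users.

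**4. Effect on the before-after comparison.** Let a share *s* of counted users be without the device, the same in both periods. Then the true percentage is (1 − s) × the observed one. With s = 0.223 and illustrative observed values of 10% and 13%:
- true values: 7.77% and 10.10%;
- ratio: 1.30 observed, 10.10 / 7.77 = 1.30 true;
- difference: 3.0 points observed, 10.10 − 7.77 = 2.33 points true.

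The ratio is unchanged and the observed difference is too large. Only a share that differs between periods would distort the ratio.

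**5. Net direction.** The closing paragraph of 9.7.2 requires only 3 months of history, so an IUD recorded before a short history is missed. Section 9.9.2 reports under-capture of contraceptives in both periods. Both errors run the other way, and no figure in the protocol lets them be netted.

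**The case against.** The strongest reply is that only the protocol is at hand and 9.7 leaves further detail to the SAP, as 9.7.3.2 does expressly for the gaps allowed within a treatment episode. Removal codes and truncation at pregnancy are operational rules of that kind. This stands for the coding detail. It does not dispose of the point, because the protocol itself sets both the window and the meaning of use, and a SAP that ended use at a delivery would be narrowing a stated definition.

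It can also be said that the measure is openly record-based and does not claim that the device is in place. That is true, but its purpose is to show contraception before treatment start, and a record contradicted by a later one does not serve that purpose.

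Pregnancy capture is incomplete: about 66% of term pregnancies in SIDIAP (9.4.2.1), possible under-reporting of induced abortions in Germany (9.4.1.2), and early terminations missing in Sweden (9.4.3.1). Table 3 limits France and Germany to reimbursed contraceptives, so a reinsertion after delivery may go unseen. This stands and limits what the fix can achieve.

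Four stronger readings are tempting, and the documents do not support them.
- **T83.3 counts a woman as protected.** The table is mixed and also holds pregnancy and delivery codes. T83.3 has its own category, the "list may be subject to amendment or revision during study conduct", and a complication diagnosis is not among the IUD data in 9.3.2. The code could equally serve to end use. Its role is simply not stated.
- **The 5-year window runs into concomitant and post-treatment use.** It is attached only to the before-treatment measure.
- **Outdated records dilute the before-after change.** Step 4 of the working shows otherwise for a constant share. The insensitivity of an old insertion to present prescribing comes from the long look-back itself and applies equally to devices still in place.
- **Contraceptive use is overstated overall.** Step 5 leaves the net direction open.

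**Conclusion.** The point holds for the before-treatment IUD measure. As written, 9.7.1 and 9.7.2 together count a woman as an IUD user on the strength of a record up to 5 years old, even when a later record shows removal, expulsion, pregnancy or delivery. Among women with a captured IUD record, the percentage is too high.

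The documents do not allow the amount to be sized. The 12, 22 and 32% rest on assumed discontinuation of 5, 10 and 15% per year and evenly spread insertions. They describe all discontinuation, whereas the correctable part is smaller and unknown. The level of the measure is what suffers. No bias in the before-after ratio is shown, and the net error after under-capture could go either way.

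**What to change.** - **Section 9.7.2:** count an IUD record as use before treatment only if no removal or expulsion record, and no later recorded pregnancy or delivery, lies between that record and the exposure start. A new insertion restarts the 5-year window. Date the later pregnancy by its start or delivery, so that a postpartum-care code (Z39) following an insertion after delivery does not end use.
- **Concomitant and post-treatment measures:** state whether earlier insertions are carried into them. If so, apply the same rule.
- **Section 9.3.3:** extend the pregnancy-record search over the IUD look-back years.
- **Annex 3.2:** state that T83.3 alone is not evidence of IUD use.

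The cost is a few lines of definition and a longer search for records the study already uses. The IUD percentage will be slightly lower. Capture of removals and pregnancies will differ by country, and some women with an uncaptured reinsertion after delivery will be counted as non-users; the report should say so.
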